### **7.3 Potential Biases Controlling**

The 5-year after CABG visit (on site) will be in person by a trained site coordinator and CRC. Original materials such as medical record and laboratory test results would be asked to provide for endpoint assessment. All potential endpoint events ( including all-cause death, cardiovascular death, non-fatal MI, non-fatal stroke, repeated coronary revascularization) will be adjudicated by an independent Clinical Endpoint Committee (CEC) according to the 2014 ACC/AHA Cardiovascular Endpoints Data Standards. Original coronary artery imagine would

be acquired if available. All grafts outcomes will be adjudicated by an independent Image Data Review Committee (IDRC) according to the DACAB protocol.

#### **7.4 Study Timetable and End of Study**

- Protocol Approved: Dec2018
- First 5-year Visit: Aug2019
- Last 5-year Visit: Dec2020
- DBL: Jun2021
- CSR: Sep2021
- Publication: Dec2021

The first 5-year visit in this study is expected in Aug 2019, while the last is in Dec 2020. Database Lock will be about 6 months after the last 5-year visit. Clinical study report is planned to be finalized in Sep 2021.

### **8. EVALUATION AND CALCULATION OF ENDPOINTS**

#### **8.1 Calculation or Derivation of Clinical Outcomes**

The primary outcome is the time to the first occurrence of any MACE-4, which is a composite of all-cause death, myocardial infarction, stroke, and coronary revascularization and measured in days since the date of randomization. Subjects who had not experienced any major adverse clinical events from randomization to the last visit will be right-censored. For those subjects who lost to follow-up at 5-year visit, the date of the last contact and the most updated clinical outcomes available in medical record or other source will be used in primary analysis. If there's no major adverse clinical events recorded for those subjects who lost to follow-up at 5-year visit, then these subjects will be right-censored at the date of their last contact. The survival curves will be estimated using Kaplan-Meier method.

The secondary outcomes (time to event) will be analyzed similarly with the primary observational endpoint.

Graft failure after CABG is in accordance with Fitzgibbon classification criteria by using MSCTA or CAG, there were a total of 3 categories, grade A, B and O, where grade B/O accounted for the graft failure.

## **9. STATISTICAL METHODS AND SAMPLE SIZE DETERMINATION**

### **9.1 Description of Analysis Sets**

Subjects will be analyzed per the randomized treatment groups they were assigned to in the previous DACAB study.

#### **9.1.1 Full Analysis Set**

The Full Analysis Set (FAS) in current study is same as FAS in DACAB trial.

#### **9.1.2 Per-protocol Set**

Per-protocol set (PPS) is defined as all subjects in the FAS with exclusion of the following subjects:

- Subject discontinued the application of study drug longer than 60 days during the treatment phase in the previous DACAB study

PPS will only be used in the analysis of primary observational endpoint. The analysis using the FAS will be regarded as primary while the analysis based on PPS will act as supportive.

## **9.2 Methods of Statistical Analyses**

### **9.2.1 General Method of Analysis**

Descriptive summary statistics, such as number of subjects, mean, SD, median, IQR, minimum, and maximum for continuous variables, and counts and percentages for discrete variables will be used to summarize data. Summary statistics will be provided for each group in previous DACAB study.

The correlations between the observational endpoints (both primary and secondary) and the characteristics of subjects will be explored, the characteristics of subject include age, gender, medical history, etc.

The missing data will be assumed missing at random, no imputation will be applied unless specified otherwise.

The detailed statistical methods applied in analyses will be provided in Statistical Analysis Plan.

#### **9.2.2 Demographics and Baseline Characteristics**

Demographic and baseline characteristic variables will be descriptively summarized by the group in previous DACAB study.

#### **9.2.3 Primary Outcome Measure**

Kaplan-Meier method will be applied to analyze the primary outcome (MACE-4), and the rate of subjects who has the first MACE-4 occurred within 1, or 2, or 3, or 4, or 5 years after CABG will be provided.

#### **9.2.4 Secondary Outcome Measures**

The time to event variables in the secondary outcomes will be analyzed similarly with the primary outcome.

As 1-4 vessels were generally measured in each subject, the vein graft patency at 5 years after CABG is a categorical data measured repeatedly in subjects. The number and the percentage of the grafts in Fitzgibbon grade B/O will be summarized by the group in previous DACAB study.

### **9.3 Determination of Sample Size**

A total of 500 subjects were randomized in DACAB study (ticagrelor + aspirin, 168; ticagrelor alone, 166; aspirin alone, 166). There are 5 subjects died before 12-month visit, of these, 2 died in ticagrelor + aspirin group, and 3 died in aspirin alone group. Therefore, 495 patients would be scheduled for 5-year on-site visit.

Statistical Analysis Plan

DACAB Trial: Follow-up Extension

(DACAB-FE)

NCT03987373

V 1.0 (2021/6/5)

[name], Doctor
Senior Statistician
Department of Biostatistics
School of Public Health
Fudan University

Date

Table of Contents

1. Background	1
2. Study Objectives	2
3. Study Design	3
4. Evaluation Indicators	4
4.1 Primary Outcome	4
4.2 Secondary Outcome	4
4.3 Evaluation and Calculation of Endpoints	5
5. Subject Selection Criteria	6
6. Statistical Analysis	6
6.1 Analysis Sets	6
6.1.1 Full Analysis Set (FAS)	6
6.1.2 Per-protocol Set (PPS)	6
6.2 Methods of Statistical Analyses	6
6.2.1 General Method of Analysis	6
6.2.2 Demographics and Baseline Characteristics	7
6.2.3 Primary Outcome	7
6.2.4 Secondary Outcome	7
6.2.5 Laboratory Indicators	8
6.2.6 Bleeding Events	8
6.2.7 Safety Events	8
6.2.8 Concomitant medications	8
6.2.9 Graft vessels cohorts	8
6.2.10 Subgroup analysis and exploratory analysis on subgroup cohorts	8
6.2.11 Data Transformation	9

6.3 Sample Size	9
7. Results of Statistical Analysis	10
 7.1 Primary and secondary objectives	10
 7.1.1 Enrollment and Baseline characteristics	10
 7.1.2 Primary Outcome	19
 7.1.3 Secondary Outcomes	21
 7.1.4 Laboratory examination during follow-up	30
 7.1.5 Concomitant medications and bleeding events	31
 7.1.6 Subgroup analysis	32
 7.2 Exploratory Objectives	35
 7.2.1 Baseline characteristics	35
 7.2.2 Major clinical events	42
7.3 Supplementary tables	46

1. *Background*

DACAB trial is an open label multi-center randomized clinical trial. The patients enrolled in DACAB trial were randomly assigned to the (1) ticagrelor+aspirin (T+A) group, (2) ticagrelor(T) group and (3) aspirin (A) group. Patients were treated and followed up for 12 months. The primary endpoint was the patency rate of saphenous vein graft (SVG) after 1 year of CABG. Secondary endpoint included MACEs within 1 year after CABG.

There are 500 patients were enrolled from July 2014 through November 2015 and follow-up was completed in January 2017, 168 patients in the T+A group, 166 in T group and 166 in A group. The results showed that the 1-year SVG patency rate (primary endpoint) of T+A group was 88.7% (432/487, T+A vs A, p=0.0006), the T group was 82.8% (371/485, T vs A, p=0.0962), and the A group was 76.5% (404/488). The incidence of MACE during 1 year of follow-up was 1.8% in T+A group, 2.4% in T group, and 5.4% in A group. The DACAB trial demonstrated that compared with aspirin monotherapy, the combination of ticagrelor and aspirin significantly improved 1-year SVG patency after CABG. Meanwhile, the combination of ticagrelor and aspirin therapy or ticagrelor monotherapy showed a favor trend with reducing the MACEs compared with aspirin monotherapy.

Would the observed differences in SVG patency at 1 year post CAGB translate into long-term clinical benefit? This remain to be a great interest to follow up these patients. Therefore, in present study, we intend to collect and analyze the long-term data in patients who were enrolled and survived in DACAB trial. We would observe the clinical outcomes of these subjects at 5-year post-CABG.

2. Study Objectives

- Primary Objective**

The primary objective is to compare the incidence of major adverse clinical events-4 (MACE-4, a composite of all-cause death, myocardial infarction, stroke, and coronary revascularization) among 3 randomized regimens in previous DACAB trial in the extended five-year follow-up after CABG.

- Secondary Objectives**

The secondary objectives are to compare the incidence of MACE-5 (a composite of all-cause death, myocardial infarction, stroke, coronary revascularization and hospitalization for unstable angina); MACE-3 (a composite of cardiovascular death, myocardial infarction and stroke); all-cause death; cardiovascular death; myocardial infarction; stroke; coronary revascularization; hospitalization for unstable angina and graft failure among 3 randomized regimens in previous DACAB trial in the five-year follow-up after CABG.

- Exploratory Objectives**

According to the imaging examination results of graft vessels at 1 year after surgery, all subjects will be divided into two natural cohorts with or without graft failure. The incidence of MACE-4, MACE-5, MACE-3, all-cause death, cardiovascular death, myocardial infarction, stroke, coronary revascularization and hospitalization for unstable angina will be compared between the two cohorts .

Similarly, all subjects will be divided into two natural cohorts with or without vein graft failure. The incidence of MACE-4, MACE-5, MACE-3, all-cause death,

cardiovascular death, myocardial infarction, stroke, coronary revascularization and hospitalization for unstable angina will be compared between the two cohorts.

The factors of planned subgroup analysis consists of gender, age stratification, ACS presentation, hypertension, diabetes mellitus, history of high low-density lipoprotein cholesterol (LDL-C), history of high lipoprotein(a), prior myocardial infarction, stroke, peripheral vascular disease, COPD, history of CKD-3 or higher, smoking, left main coronary artery disease, SYNTAX Score stratification, EuroScore stratification at baseline, on-pump or off-pump, whether to use the internal thoracic artery, complete revascularization or not.

In addition to subgroup analysis according to random grouping, the subjects will also be divided into corresponding natural cohorts according to different levels of subgroups, and the incidence of MACE-4, MACE-5, MACE-3, all-cause death, cardiovascular death, myocardial infarction, stroke, coronary revascularization and hospitalization for unstable angina will be compared between the cohorts.

3. Study Design

The primary objective of this study is to observe the clinical outcomes of subjects at 5-year post-CABG. The DACAB study was designed as a multi-center, prospective, open label, evaluator blind, randomized controlled trial.

4. Evaluation Indicators

4.1 Primary Outcome

MACE-4, defined as a composite of all-cause death, myocardial infarction, stroke, and coronary revascularization. The outcome measure is the time to the first occurrence of MACE-4 event from randomization to the last visit.

4.2 Secondary Outcome

- MACE-5, defined as a composite of all-cause death, myocardial infarction, stroke, coronary revascularization and hospitalization for unstable angina. The outcome measure is the time to the first occurrence of MACE-5 event from randomization to the last visit;
- MACE-3, defined as a composite of cardiovascular death, myocardial infarction and stroke. The outcome measure is the time to the first occurrence of MACE-3 event from randomization to the last visit;
- All-cause death. The outcome measure is the time to the first occurrence of all-cause death from randomization to the last visit;
- Cardiovascular death. The outcome measure is the time to the first occurrence of cardiovascular death from randomization to the last visit;
- Myocardial infarction. The outcome measure is the time to the first myocardial infarction from randomization to the last visit;
- Stroke. The outcome measure is the time to the first stroke from randomization to the last visit;
- Coronary revascularization. The outcome measure is the time to the first coronary revascularization from randomization to the last visit.;

- Hospitalization for unstable angina. The outcome measure is the time to the first hospitalization for unstable angina from randomization to the last visit;
- Graft failure/vein graft failure at the last visit (Fitzgibbon Grade B/O assessed by CCTA or CAG). The outcome measure is the incidence of graft failure/vein graft failure.

4.3 Evaluation and Calculation of Endpoints

The primary outcome is the time to the first occurrence of any MACE-4, which is a composite of all-cause death, myocardial infarction, stroke, and coronary revascularization and measured in days since the date of randomization. Subjects who had not experienced any major adverse clinical events from randomization to the last visit will be right-censored. For those subjects who lost to follow-up at 5-year visit, the date of the last contact and the most updated clinical outcomes available in medical record or other source will be used in primary analysis. If there's no major adverse clinical events recorded for those subjects who lost to follow-up at 5-year visit, then these subjects will be right-censored at the date of their last contact. The survival curves will be estimated using Kaplan-Meier method.

The secondary outcomes (time to event) will be analyzed similarly with the primary observational endpoint.

Graft failure after CABG is in accordance with Fitzgibbon classification criteria by using MSCTA or CAG, there were a total of 3 categories, grade A, B and O, where grade A accounted for graft patency (no lesions), and grade B/O accounted for the graft failure.

5. Subject Selection Criteria

All the subjects enrolled in the DACAB trial.

6. Statistical Analysis

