## **5.2 Data Collection at 5-year Visit**

The data of subjects will be collected at the visit at 5-year ( $\pm 3$  month) after CABG. The collected data includes: vital signs; current medications; types and time of events; original medical record and laboratory test results related to clinical events. For deceased patients, the death and cause of death will be determined by telephone interview with their relatives firstly. The related medical records would be acquired from their relatives to further determination the cause of death, if available. Electronic medical records would be approached under relatives' permission. Determination of graft patency will be determined from medical records. Original images of coronary CTA or coronary angiography will be acquired and re-assessment.

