### **5.3.2 Secondary Outcome Measures**

Including:

- 1) MACE-5, defined as a composite of all-cause death, myocardial infarction, stroke, coronary revascularization and hospitalization for unstable angina. The outcome measure is the time to the first occurrence of MACE-5 event from randomization to the last visit.
- 2) MACE-3, defined as a composite of cardiovascular death, myocardial infarction and stroke. The outcome measure is the time to the first occurrence of MACE-3 event from randomization to the last visit.
- 3) All-cause death. The outcome measure is the time to the first occurrence of all-cause death from randomization to the last visit.
- 4) Cardiovascular death. All “undetermined death” will be assumed as “cardiovascular death”. The outcome measure is the time to the first occurrence of cardiovascular death from randomization to the last visit.
- 5) Myocardial infarction, including STEMI, NSTEMI, or silent/unrecognized MI (eg. new pathological Q waves detected by ECG, or new reduced ventricular wall motion detected by UCG during follow-up). The outcome measure is the time to the first myocardial infarction from randomization to the last visit.
- 6) Stroke, including ischemic, hemorrhagic, or unknown type. The outcome measure is the time to the first stroke from randomization to the last visit.
- 7) Coronary revascularization, any repeated PCI or CABG, no matter ischemic driven or not. The outcome measure is the time to the first coronary revascularization from randomization to the last visit.
- 8) Hospitalization for unstable angina. The outcome measure is the time to the first hospitalization for unstable angina from randomization to the last visit.
- 9) Graft failure/vein graft failure at the last visit (Fitzgibbon Grade B/O assessed by CCTA or CAG). The outcome measure is the incidence of graft failure/vein graft failure.

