6.2 Methods of Statistical Analyses

6.2.1 General Method of Analysis

Counts and percentages for discrete variables, and mean, SD, maximum, minimum, median, 25th percentiles and 75th percentiles for continuous

variables will be used to summarize data.

The missing data will be assumed missing at random, no imputation will be applied unless specified otherwise.

A 2-sided level of significance of .05 will be applied to all statistical analyses unless specified otherwise. Statistical analyses will be performed using SAS 9.4.

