6.2.4 Secondary Outcome

The time to event variables in the secondary outcomes will be analyzed similarly with the primary outcome.

As 1-4 vessels were generally measured in each subject, the vein graft patency at 5 years after CABG is a categorical data measured repeatedly in subjects. The number and the percentage of the grafts in Fitzgibbon grade B/O will be summarized by the group in previous DACAB study. GEE (Generalized Estimating Equations) was used to compare the subjects' saphenous vein graft patency rate among groups.

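### The 5-year graft-failure grade takes no account of earlier intervention, so under the rule as written a failed graft that was re-opened by PCI and is lesion-free when imaged would count as patent

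*SAP*

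**What the plan says.** Protocol 5.3.2, item 9, lists as a secondary outcome "Graft failure/vein graft failure at the last visit (Fitzgibbon Grade B/O assessed by CCTA or CAG"), and names its measure as the incidence of graft failure. SAP 4.2 repeats this. Protocol 8.1 defines failure as grade B or O. SAP 4.3 adds the other half: "where grade A accounted for graft patency (no lesions), and grade B/O accounted for the graft failure".

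For the data source, protocol 5.2 says "Determination of graft patency will be determined from medical records", and adds that original CTA or angiography images will be obtained and re-assessed. Protocol 7.3 says "All grafts outcomes will be adjudicated by an independent Image Data Review Committee (IDRC) according to the DACAB protocol".

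For the analysis, SAP 6.2.4 says "The number and the percentage of the grafts in Fitzgibbon grade B/O will be summarized by the group", and then "GEE (Generalized Estimating Equations) was used to compare the subjects' saphenous vein graft patency rate among groups". Table 13 (SAP 7.1.3) reports rate differences, risk ratios and p-values for the three pairs of arms, including a window of 1 to 5 years after surgery. SAP 6.2.1 sets the test level: "A 2-sided level of significance of .05 will be applied to all statistical analyses unless specified otherwise".

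Repeat procedures are collected separately. Coronary revascularization is "any repeated PCI or CABG, no matter ischemic driven or not" (protocol 5.3.2, item 7), and it is also a component of MACE-4 and MACE-5. Nothing links that record to the grade of a particular graft.

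**The concern.** An incidence counts grafts that have failed at any time. A grade at the last visit describes how the graft looks then. The two differ for a graft that fails and is treated in between, and the plan does not say which one applies.

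The case can be expected to arise. After month 12 the study leaves treatment to the attending physicians, and imaging follows clinical need (protocol 3.1). Repeat PCI and CABG are anticipated as outcomes. The protocol's own Table 1 cites a study in which vein-graft failure was followed by more revascularization.

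If such grafts are graded only as imaged, the treatment given for a failure removes that failure from the endpoint. A redo operation leaves a second gap: no rule covers an index graft that is replaced or re-bypassed, and none says whether a new conduit counts. Table 32 (SAP 7.2.2), which sets 1-year grade against 1-to-5-year grade, would then contain grafts that move from failed to patent with nothing to explain them.

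At stake are the patency rates in each arm and the between-arm estimates and p-values in Table 13.

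**Working it through.** **1. The plan's own graft figures.** The documents give vein-graft patency at 1 year only (protocol 1.1; SAP 1):
- T+A: 432/487 = 88.7%, as printed.
- T: printed as 82.8% beside 371/485, but 371/485 = 76.5%.
- A: printed as 76.5% beside 404/488, but 404/488 = 82.8%.

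The T and A fractions stand beside each other's percentages. Exchanging them reproduces both. The stated p = 0.0006 for T+A against A supports the percentages. A simple pooled z-test that ignores clustering gives p of about 5 × 10⁻⁷ with A at 76.5%, and about 0.008 with A at 82.8%. Allowing for clustering of grafts within patients would normally raise p, so only the first is compatible with 0.0006. The crossed fractions are a separate correction to make.

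Failure at 1 year is therefore A 114/485 = 23.5%, T 84/488 = 17.2%, T+A 55/487 = 11.3%.

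**2. What is not given.** The documents state no 5-year failure rate, no power for this endpoint and no re-opening rate. Below, the 1-year failure rates stand in for true failure. The share r of failed grafts that are re-opened and then graded A is assumed, from 0% to 30%.

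**3. Formulas**, for true failure f and re-opened share r in each arm:
- Observed failure: f′ = f(1 − r).
- Difference: D′ = f_A(1 − r_A) − f_TA(1 − r_TA). With equal r this is (1 − r) × D.
- Failure RR: RR′ = RR × (1 − r_TA)/(1 − r_A). With equal r this is unchanged.
- Patency RR (Table 13 is set out in patency rates): (1 − f′_TA)/(1 − f′_A).

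**4. Results** (differences computed before rounding):

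| r in A | r in T+A | Failure A | Failure T+A | Difference (points) | Failure RR | Patency RR |
|---|---|---|---|---|---|---|
| 0% | 0% | 23.5% | 11.3% | 12.2 | 0.48 | 1.16 |
| 10% | 10% | 21.2% | 10.2% | 11.0 | 0.48 | 1.14 |
| 20% | 20% | 18.8% | 9.0% | 9.8 | 0.48 | 1.12 |
| 30% | 30% | 16.5% | 7.9% | 8.5 | 0.48 | 1.10 |
| 20% | 10% | 18.8% | 10.2% | 8.6 | 0.54 | 1.11 |
| 30% | 10% | 16.5% | 10.2% | 6.3 | 0.62 | 1.08 |
| 10% | 20% | 21.2% | 9.0% | 12.1 | 0.43 | 1.15 |
| 10% | 30% | 21.2% | 7.9% | 13.2 | 0.37 | 1.17 |

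At r = 20% in every arm, the grafts moved from failed to patent number 114 × 0.2 = 22.8 in A, 84 × 0.2 = 16.8 in T and 55 × 0.2 = 11.0 in T+A.

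**5. Direction.** D′ is smaller than D when f_A × r_A exceeds f_TA × r_TA. With these rates, that means the T+A share is less than 23.5/11.3 = 2.1 times the A share. The failure RR moves away from 1 as soon as r_TA exceeds r_A. The two measures can therefore move in opposite senses: at 10% in A and 20% in T+A, the difference falls slightly while the failure RR goes from 0.48 to 0.43.

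**The case against.** The strongest objection is that the documents are silent; they do not state a wrong rule. A reader might infer that the plan classes re-opened grafts as Grade A. No sentence says so. Adjudication is delegated to the DACAB protocol, which may cover treated grafts, and a stented segment is not self-evidently free of lesions. This stands, and it is why the point is conditional. It does not remove the gap. The parent trial's treatment and follow-up lasted 12 months, this endpoint adds the years of unrestricted care after that, and neither current document states or cites a specific rule.

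A second objection is that the documents speak of the last visit, not the last scan, and that Tables 12 and 13 use a 1-to-5-year window. An angiogram taken when the graft was treated falls in that window and could itself be graded B or O. This also stands. It shows that the result depends on which of several scans is used, and the plan does not say.

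A reader might also infer that failures are hidden mostly in the aspirin arm and that the treatment difference must shrink. The documents do not support that. It follows only if re-opening shares are similar, and nothing in them gives the shares. With equal shares the failure RR does not move at all, and with 10% in A and 30% in T+A the difference widens.

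Finally, one procedure can be an event in Table 5 and leave a patent graft in Table 13. That alone is not a contradiction: MACE-4 is counted per patient, and a clinical event and an anatomical status may legitimately differ.

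**Conclusion.** The concern holds in conditional form. As written, the grade ignores earlier intervention, and nothing in the protocol or SAP prevents a failed, re-opened, lesion-free graft from counting as patent over years 1 to 5. If the DACAB protocol has no rule for this, failure is understated in any arm where such grafts occur.

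With equal re-opening shares, the rate difference shrinks by (1 − r), the patency RR moves towards 1 and the failure RR is unchanged. With unequal shares the bias can go either way. The figures above illustrate this with 1-year failure rates and assumed shares; they do not estimate the 5-year bias, whose size the documents do not allow anyone to find.

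The reach is limited to a secondary endpoint. The primary MACE-4 analysis counts the revascularization itself and is not affected. The exploratory cohorts are formed from 1-year imaging, so the gap touches them only where a graft was re-opened before that scan. The point should be settled before the graft analysis is run, because Table 13 reports formal between-arm comparisons.

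**What to change.** State the following in protocol 8.1 and SAP 4.3:
- An index study graft that had PCI to that graft, or was replaced or re-bypassed at redo CABG, before the imaging used is classified as failed.
- Grafts placed after the index operation are excluded.
- Which scan is used when a graft has several in the 1-to-5-year window.
- The as-imaged grade is reported as a sensitivity analysis.

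If the DACAB protocol already contains such a rule, cite it and quote it in the SAP.

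The cost is a few sentences and some record work. Protocol 5.2 collects the types and times of events with their source records and images, but describes no field for which graft was treated. The treated graft must therefore be identified from revascularization records and images already collected, which may mean re-reading some of them. Reported patency will be slightly lower, and the main endpoint becomes imaging or intervention rather than imaging alone. The as-imaged sensitivity analysis keeps the purely anatomical result available.
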